1. BACKGROUND

1.1. BROADBAND LIGHT TREATMENT

Broadband light (BBL) is a comprehensive phototherapy system that incorporates dual flashlamp technology, interchangeable filters, snap on adapters, and a precise thermoelectric cooling system for treatment that is safe, effective, with a high ease of use. BBL treatment uses intense pulses of non-coherent light over an approximate 400 – 1400 nanometers (nm) wavelength range. Dual Xenon flash lamps produce high output bursts of broad spectrum light. Various cutoff filters are available to filter out specific frequencies and narrow the spectrum of light to target specific chromophores in the skin. Adjustable cooling is also provided to protect the skin surface in contact with the device.

Broadband light (BBL) treatment has been widely used in dermatologic applications for improvement in rosacea and acne. To address rosacea, BBL can be filtered to deliver wavelengths of light that are absorbed by hemoglobin to result in damage to the vessels that are responsible for the visible flushing seen in rosacea. Controlled injury to the blood vessels may initiate the body's natural response to breakdown and remove the damaged vessels. As an acne treatment, a BBL filter can be selected to target the bacteria *Propionibacterium acnes* which causes acne. *Propionibacterium acnes* absorbs the light energy, resulting in the selective destruction of bacteria.

The well characterized effects of BBL treatment to improve rosacea and acne will be applied to the symptoms of DED. Chronic inflammation of the eyelids and conjunctiva is proposed to be one of the major causes of DED. BBL treatment can alleviate inflammation by removing the bacteria from the eyelids and eyelashes. BBL can also diminish telangiectasias, which are correlated with DED. Removal of telangiectasias and excess blood vessels around the eye can decrease the cytokines and inflammatory mediators in the eye region.

2. STUDY RATIONALE

2.1. RESEARCH HYPOTHESIS

Broadband light (BBL) treatment is safe and provides improvement in the symptoms of refractory dry eye disease (DED).

2.2. RATIONALE

With an estimated prevalence of 7-33%, DED is a frequently encountered ocular morbidity, resulting in a \$3.8 billion economic burden on the USA healthcare system. The meibomian glands, located in the upper and lower eye lids, produce the tear film. Evaporative dry eye occurs from the disruption of the top layer of the tear film. Bacteria occurring on the eyelashes or within the meibomian glands can result in chronic irritation and inflammation, subsequently causing meibomian gland dysfunction (MGD).

Broadband Light (BBL) technology is FDA cleared for indications including rosacea and the improvement of cutaneous vascular lesions. BBL may alleviate DED symptoms by reducing inflammatory blood vessels and by improving meibomian gland function, thereby providing an effective DED treatment with a high safety profile.

**THE SAFETY AND EFFICACY OF BROADBAND LIGHT (BBL) TREATMENT
FOR REFRACTORY DRY EYE DISEASE (DED)**

3. CRITERIA FOR SUBJECT SELECTION

3.1. NUMBER OF SUBJECTS

In this prospective study to determine safety and efficacy, a minimum of twenty subjects will be treated to detect improvement after BBL treatment for DED.

3.2. STUDY POPULATION

Subjects that are aged eighteen years or older with refractory DED will be enrolled in the study. Refractory will be defined as having persistent dry eye signs and or symptoms after at least one prior DED treatment modality. Subjects of both genders will be included in study enrollment. Only English speaking subjects will be enrolled.

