3.3. INCLUSION CRITERIA

A subject will be eligible for inclusion in the study if ALL of the following criteria apply:

- Aged eighteen or older
- Having Fitzpatrick Skin Type I-V
- Must be diagnosed with DED and meibomian gland dysfunction (MGD)
- Persistent dry eye signs and or symptoms after at least one prior DED treatment modality
- Must be willing and able to adhere to the study schedule and protocol requirements
- Signed the informed consent form prior to any study related procedure

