3.4. EXCLUSION CRITERIA

The subject will not be eligible for inclusion in the study if ANY of the following criteria apply:

- Prior IPL treatment for DED within the past six months
- Prior Lipiflow treatment for DED within the past three months
- History of trauma-induced ocular surface disease (thermal burns, chemical burns)
- Subject is pregnant
- History of seizures
- Having significant unprotected sun exposure within the treatment area
- Use of Accutane within the last six months
- Use of doxycycline in the last 1 month
- Allergy to proparacaine or lidocaine
- Having active herpes simplex virus infection within the treatment area
- Laser eye surgery (LASIK) within the past twelve months
- History of abnormal response to sunlight
- Having an active medical condition that may affect normal healing
- Having active infections or compromised immune system
- History of basal cell carcinoma in the treatment area within the past twelve months
- History of keloid scar formation

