5.1. SCREENING (TWO WEEKS)

Subject screening (study week minus two weeks) is designed to determine whether the subjects are eligible for study enrollment and to facilitate completion of the run-in period. The Clinical Investigator and study staff will recruit subjects by offering participation to existing patients at the evaluation site and by referrals. Eligible subjects are defined as those that meet all the Inclusion Criteria and meet none of the Exclusion Criteria. During subject screening and enrollment the following information will be collected:

- Evaluation of subject eligibility
- Fitzpatrick skin type
- A complete medical history
- A complete ophthalmic history
- Information on all concomitant medications

THE SAFETY AND EFFICACY OF BROADBAND LIGHT (BBL) TREATMENT FOR REFRACTORY DRY EYE DISEASE (DED)

- Clinical photographs of face, eyes, and meibomian glands before treatment
- Persistent dry eye signs and or symptoms after at least one prior DED treatment modality
- Signed Informed Consent Form

At the discretion of the Clinical Investigator, subjects who fail screening may be re-screened once, at a later date once the subject has met the criteria. The Clinical Investigator or study staff will obtain the signed informed consent form before any study specific procedures are performed. Each subject will be assigned a unique screening number, which will correspond to his/her unique enrollment identification number.

Potential subjects will be given ample time to ask questions and get their questions answered in regards to their participation in the study. The questions will be answered in a manner that is understandable to the subject. Subjects will be told that whether or not they choose to participate in the study, it will not affect their relationship with their physician.

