After eligibility is confirmed the subject will immediately proceed to the run-in phase. This phase will be completed to ensure complete collection of subject baseline values. Subjects will be instructed not to use any artificial tears for at least 2 hours before testing. They will also be instructed to continue any over-the-counter habitual artificial tears at the same frequency and will be instructed not to change any of their current therapy for their DED. All subjects will undergo a full ophthalmic exam and DED diagnostic testing, which will include clinical evaluations for Dry eye: All sites will perform osmolarity, and Inflammadry test strips for level of MMP-9, staining pattern on cornea (using oxford scale) with Fluorescein, Tear Break Up Time (TBUT), 5 minute Schirmer's testing with anesthesia. USC site will obtain swabs for evaluation of ocular surface microbiome, to be sent to a core facility.

Additionally, clinical photographs of the face, eyes, and meibomian glands will also be collected, and subjects will complete DED questionnaires (SPEED and VAS). All subjects will undergo BBL treatment for a series of 3 treatments after being randomized to treatment protocol 1 or 2 (protocol 1 includes 420nm and 560nm treatment settings, protocol 2 includes only 560nm treatment settings, see Table 2 below). To demonstrate effects of DED treatments, baseline values will later be compared to values following treatment.

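### Entry requires no period of unchanged DED therapy before baseline, so delayed benefit from a recently added therapy can be counted as BBL effect

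*Protocol*

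**What the plan says.** - **Entry rule.** Protocol 3.2: "Refractory will be defined as having persistent dry eye signs and or symptoms after at least one prior DED treatment modality". The inclusion criterion in 3.3 repeats it: "Persistent dry eye signs and or symptoms after at least one prior DED treatment modality". Section 4 gives the definition a third time and adds that the subject has failed the prior modality. None of the three mentions a period of unchanged therapy before screening or baseline.
- **Recency exclusions.** Section 3.4 has four for treatments: "Prior IPL treatment for DED within the past six months", "Prior Lipiflow treatment for DED within the past three months", "Use of doxycycline in the last 1 month" and "Use of Accutane within the last six months". No other DED drop, lid regimen or device has a window.
- **Background therapy on study.** Section 5.1 says that subjects "will be instructed not to change any of their current therapy for their DED", and that habitual artificial tears continue at the same frequency.
- **Run-in.** Section 5.1 gives its purpose as completing the collection of baseline values, not stabilising therapy.
- **Data at screening.** The list in 5.1 includes "Information on all concomitant medications" and the medical and ophthalmic histories. It does not list start or change dates.
- **Analysis.** The SAP compares mean scores at enrollment and after three sessions over all patients, with a Student's t test at p<0.05. Both randomised protocols deliver BBL.

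**The concern.** The instruction in 5.1 prevents new changes once a subject is in the study. It does nothing about a therapy begun shortly before. If that therapy takes weeks to act, holding it constant keeps its later benefit inside the before/after difference. The "before" value is taken at enrollment, so the two run-in weeks also belong to the measured change.

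Nothing in the analysis can remove this. There is no arm without BBL, randomisation is between two BBL protocols, and the SAP plans no adjustment or sensitivity analysis by background therapy. If the added therapy helps, the bias favours BBL. The plan already treats recent therapy as a problem for the treatments named in 3.4; the gap is the remaining DED therapies.

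**Working it through.** **1. The stated sample size.** Section 3.1 gives a minimum of 20 subjects but no effect size, SD or power, so the figure cannot be reproduced. For scale, a paired t test with n = 20 at two-sided 5% has 80% power for a mean change of 0.66 SD and 90% for 0.76 SD (SD of the within-patient change, noncentral t).

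**2. Length of the before/after window.** Two weeks from screening to first treatment (Section 4), two intervals of 3-5 weeks (5.2), and four weeks to follow-up (5.3):

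- shortest: 2 + 2 × 3 + 4 = 12 weeks
- at four-week spacing: 2 + 2 × 4 + 4 = 14 weeks
- longest: 2 + 2 × 5 + 4 = 16 weeks

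**3. Size of the bias.** Let *f* be the share of recent starters and *g* their mean improvement after baseline from the added therapy, in SDs of the change score. With no BBL effect, the expected mean change is *f* × *g*. The documents give neither quantity. I assume *f* = 10-30% and *g* = 0.5-1.0, so the shift runs from 0.10 × 0.5 = 0.05 SD to 0.30 × 1.0 = 0.30 SD.

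**4. Effect on the test.** Simulation with n = 20, of whom 20 × *f* = 2, 4 or 6 have mean *g* and the rest mean zero, unit SD, t = mean / (SD/√20), critical value 2.09 on 19 df. The SAP does not say that the test is paired or two-sided; both are assumed. The table gives the probability of a significant result in the direction of improvement on one endpoint; the nominal value is 0.025.

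| Recent starters | Shift at *g* = 0.5 | P(significant) | Shift at *g* = 1.0 | P(significant) |
|---|---|---|---|---|
| 10% (2 of 20) | 0.05 | 0.038 | 0.10 | 0.054 |
| 20% (4 of 20) | 0.10 | 0.059 | 0.20 | 0.106 |
| 30% (6 of 20) | 0.15 | 0.083 | 0.30 | 0.189 |

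Counting both tails against a nominal 0.05, a share of 10% gives about 0.05-0.06 and 25% gives 0.08-0.14. A share of 50%, which is extreme, gives 0.17-0.47.

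**5. With stable therapy.** If background therapy were stable long enough to produce no further change, *f* × *g* = 0 and this source of error disappears. The documents do not give the length needed, so none is computed.

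**The case against.** The strongest reply is that the entry rule is not as loose as it looks. A reader might infer that someone a few days into a first drop counts as refractory. Section 4 speaks of subjects who have failed a prior modality and already need treatment for refractory disease, and the investigator judges eligibility. Although no minimum duration is written, that wording sits badly with the extreme case. This stands. The likeliest route is narrower: a patient who failed one modality and recently added another.

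A reader might also infer that such benefit is in fact counted as BBL effect. The documents do not support that, because they show neither that recent starters will enroll nor that they will improve after baseline.

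Three further replies have weight:

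- The instruction to keep therapy unchanged appears in the run-in text with no stated end. That it runs to follow-up is the natural reading, but an inference.
- The effect may be small. With 10% recent starters the upper-tail rate is only 3.8-5.4%, and the largest assumed shift is under half the detectable change (0.30 / 0.66 = 0.45).
- The root limitation is the lack of an arm without BBL. Regression to the mean and placebo response would survive any stability rule.

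None of these closes the gap. That other biases remain is no reason to leave one that can be reduced without adding an arm. Section 4 does appear to place examinations and questionnaires at treatment visits before BBL, so a second pre-treatment measurement may exist. Comparing it with screening would show drift over the first two weeks, but not over the 10-14 weeks that follow.

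**Conclusion.** The gap is real and its size is unknown. No statement of the entry rule requires unchanged DED therapy before baseline, the exclusions cover four named treatments, and the pooled before/after test cannot separate BBL from delayed benefit of another therapy. Such benefit can be counted as BBL effect.

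The 4-19% range for a spurious improvement, against 2.5%, rests on the assumed share and improvement, a paired two-sided test, n = 20, one endpoint and no BBL effect. With few recent starters the inflation is slight. The point merits a change because the remedy is cheap, not because a large bias has been shown.

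**What to change.** 1. At screening, record start and last-change dates for every DED therapy. The current list in 5.1 does not include them, so this is a small addition to data collection.
2. Add to the SAP a sensitivity analysis that repeats the before/after comparisons without patients whose DED therapy was started or changed within a prespecified window before enrollment.
3. Preferably, require in 3.2, 3.3 and Section 4 alike that current DED therapy be unchanged for a stated period before screening. The sponsor should choose and justify the length. The Lipiflow window in 3.4 follows a device procedure and cannot simply be borrowed for drops or lid regimens. The new clause must be reconciled with the windows in 3.4: for example, a clause that also covers stopped therapy could exclude a patient whom the doxycycline criterion admits.

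The cost is slightly slower entry for some patients and a sensitivity set smaller than an already small sample. Regression to the mean and placebo response would remain, and the report should say so.

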3.3. INCLUSION CRITERIA

A subject will be eligible for inclusion in the study if ALL of the following criteria apply:

- Aged eighteen or older
- Having Fitzpatrick Skin Type I-V
- Must be diagnosed with DED and meibomian gland dysfunction (MGD)
- Persistent dry eye signs and or symptoms after at least one prior DED treatment modality
- Must be willing and able to adhere to the study schedule and protocol requirements
- Signed the informed consent form prior to any study related procedure

3.4. EXCLUSION CRITERIA

The subject will not be eligible for inclusion in the study if ANY of the following criteria apply:

- Prior IPL treatment for DED within the past six months
- Prior Lipiflow treatment for DED within the past three months
- History of trauma-induced ocular surface disease (thermal burns, chemical burns)
- Subject is pregnant
- History of seizures
- Having significant unprotected sun exposure within the treatment area
- Use of Accutane within the last six months
- Use of doxycycline in the last 1 month
- Allergy to proparacaine or lidocaine
- Having active herpes simplex virus infection within the treatment area
- Laser eye surgery (LASIK) within the past twelve months
- History of abnormal response to sunlight
- Having an active medical condition that may affect normal healing
- Having active infections or compromised immune system
- History of basal cell carcinoma in the treatment area within the past twelve months
- History of keloid scar formation

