## Broadband Light for Refractory Dry Eye Disease Statistical Analysis Plan

The SPEED validated dry eye disease questionnaire and visual analog scale will be given to patients at time of enrollment and after three sessions, the mean score before and after treatment for all patients will be calculated along with standard deviation and a student's T test will be used to assess whether there is a significant difference ( $p<0.05$ ).

The same will be done for numbers such as tear osmolarity, basal tear production test times, tear break-up times. The proportion of patients in each category of the oxford scale for fluorescein grading (I-V) will also be compared at baseline and post-treatment and the change in grade of individual patients will be assessed descriptively.

For the microbiome portion of the study, swabs from the ocular surface and lid margin will be obtained, in addition to facial skin and environmental control, at baseline and after treatment. 16S ribosomal DNA sequencing will be performed to generate an amplicon sequence variant (ASV) table using DADA2. Briefly, DADA2 performs quality filtering, de-noising, sample inference, and chimera removal using an empiric error model to generate exact amplicon sequences. Next, taxonomies will be assigned to each sequence variant using the RDP naïve Bayes classifier. The 'decontam' R package

(<https://www.biorxiv.org/content/early/2017/11/17/221499>) will be used to remove contaminant sequences based on the composition of negative controls including both DNA extraction buffers and PCR negatives.

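### Antibiotic use other than recent doxycycline is neither dated nor handled in the before/after microbiome analysis, so some antibiotic-related change can be credited to BBL

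*Protocol*

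**What the plan says.** **Entry.** Protocol 3.4 names one antibiotic: "Use of doxycycline in the last 1 month". The nearest other criterion, "Having active infections or compromised immune system", concerns infection rather than drug exposure. Protocol 3.3 requires "Persistent dry eye signs and or symptoms after at least one prior DED treatment modality" and does not limit what that earlier treatment was.

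**During the study.** Protocol 5.1 says that patients "will be instructed not to change any of their current therapy for their DED". The same section lists "Information on all concomitant medications" among the items collected at screening. Neither the treatment visits (Protocol 4 and 5.2) nor the follow-up visit (Protocol 5.3) lists a medication update.

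**Mechanism and microbiome test.** Protocol 1.1 proposes that "BBL treatment can alleviate inflammation by removing the bacteria from the eyelids and eyelashes". The SAP examines bacterial composition by 16S sequencing: "swabs from the ocular surface and lid margin will be obtained, in addition to facial skin and environmental control, at baseline and after treatment". Its methods are alpha and beta diversity comparisons, PERMANOVA, ZINB regression by site and treatment, and random forest classification. None has an antibiotic term, exclusion or sensitivity analysis.

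**The concern.** An antibiotic changes the same thing that the microbiome swabs measure. Two situations fall outside the plan's safeguards:

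- **A course finished shortly before the baseline swab.** The flora may recover during the study whatever BBL does. That could look like a BBL effect on diversity, or hide a real reduction.
- **An antibiotic started or stopped during the study for a reason other than DED**, such as acne, rosacea or an intercurrent infection. A course close to the follow-up swab acts in the direction the protocol hypothesises for BBL. The doxycycline criterion applies at entry, so it does not cover doxycycline begun later for such a reason.

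Both randomised protocols deliver BBL, so no untreated patients show what the flora would have done anyway. At stake is the interpretation of the before/after microbiome results. If exposure is not recorded with dates at the time, it may not be recoverable later.

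**Working it through.** The plan states no figure on this point, so there is nothing to reproduce. The check has three parts.

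**1. Which exposures do the safeguards cover?**

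| Exposure | Safeguard | Covered? |
|---|---|---|
| Doxycycline in the month before entry | Protocol 3.4 | Yes |
| Another antibiotic, current at entry, for an active infection | Protocol 3.4, infection criterion | Largely |
| Another antibiotic, used for DED and continued unchanged | Protocol 5.1, stable DED therapy | Largely, for a before/after change |
| Another antibiotic, finished shortly before the baseline swab | None; the screening medication list need not capture it with dates | No |
| An antibiotic started or stopped during the study for a non-DED reason | None; no medication update after screening | No |

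The environmental and negative controls with the decontam step deal with contaminating sequences, and the false discovery rate adjustment deals with multiplicity. Neither deals with drug exposure. Randomisation balances antibiotic use between the two protocols on average, but does not protect a before/after comparison.

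**2. How long is the window?** The inputs are two weeks from screening to first treatment (Protocol 4), three treatments 3 to 5 weeks apart, hence two gaps (Protocol 5.2), and four weeks to follow-up (Protocol 5.3).

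- Shortest: 2 + 2 × 3 + 4 = 12 weeks
- Longest: 2 + 2 × 5 + 4 = 16 weeks

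That leaves room for flora to recover after an earlier course, or for a new course to be taken.

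**3. How much could it matter? (illustration on assumed inputs)** The documents give no antibiotic-use rate and no variance for any microbiome measure. Assume that all 20 patients (the Protocol 3.1 minimum) are swabbed, that the true BBL effect is zero, and that k patients have an antibiotic-related shift of d SD, all in one direction, in a diversity index. A pre/post correlation of 0.5 is assumed for the rank-sum test, which makes the SD of the change √(2 − 2 × 0.5) = 1 SD of the index. The bias in the mean change is k × d / 20. For k = 4 and d = 1 it is 4 × 1 / 20 = 0.20 SD. Simulated two-sided rejection rates at 0.05:

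| k | d (SD) | Bias (SD) | Paired t test | Rank-sum test |
|---|---|---|---|---|
| 0 | – | 0 | about 5% | under 1% |
| 2 | 0.5 | 0.05 | 5.6% | 0.8% |
| 2 | 1.0 | 0.10 | 6.0% | 1.0% |
| 2 | 1.5 | 0.15 | 6.9% | 1.4% |
| 4 | 0.5 | 0.10 | 6.5% | 1.2% |
| 4 | 1.0 | 0.20 | 10.7% | 2.0% |
| 4 | 1.5 | 0.30 | 15.7% | 4.2% |
| 6 | 0.5 | 0.15 | 8.8% | 1.8% |
| 6 | 1.0 | 0.30 | 18.8% | 5.7% |
| 6 | 1.5 | 0.45 | 30.7% | 13.4% |

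The paired t test used 20,000 runs. The rank-sum test used 2,000, so its rates are good to about a percentage point. The rank-sum test, which the SAP names, starts well below 5% here because it ignores the pairing; that is conservatism, not protection against confounding. PERMANOVA, ZINB and random forest were not simulated.

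**The case against.** **The existing safeguards do much of the work.** In part this stands. Current medications and full medical and ophthalmic histories are taken at screening, active infection is excluded, and current DED therapy is held constant. A reader might infer that anyone taking another antibiotic contaminates the comparison. The documents do not support that: an antibiotic used for DED and continued unchanged should not itself produce a before/after change. What remains is the recently finished course and the non-DED antibiotic started or stopped during the study.

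**The distortion is small.** This stands for plausible small numbers on the test that the SAP names. With up to four of 20 exposed, the rank-sum rejection rate stays below 5% in the illustration. The paired t test, which reaches about 11% to 16% with four exposed at 1 to 1.5 SD, is not planned for these data. Recovery and new courses also act in opposite directions; if exposures split evenly, the mean bias cancels. A reader might infer that a few exposed patients would drive the taxon-level and random forest findings. Nothing in the documents or the illustration shows that. The number swabbed is itself unclear: Protocol 4 describes one site, while Protocol 5.1 refers to all sites and says "USC site will obtain swabs for evaluation of ocular surface microbiome, to be sent to a core facility".

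**The lack of an untreated group is a general limitation, and the microbiome is not the main question.** Both are true. The research hypothesis (Protocol 2.1) concerns safety and symptoms, and the SAP leads with SPEED and VAS. But this particular source of change can be measured and set aside cheaply, which is not so for most limitations of a before/after design.

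**The doxycycline criterion should simply be widened.** A reader might infer that it is an inadequate microbiome control and that a broader washout is required. The documents do not say why doxycycline is excluded, or that one month restores the flora. Which drugs must be stopped, and for how long, is a clinical decision and none is proposed here.

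**Conclusion.** The point holds in a limited form. As written, the plan keeps patients with a recently finished or newly changed antibiotic in the before/after microbiome analysis. It does not record the dates needed to identify them, and it has no untreated patients to show the change without BBL. An antibiotic effect, or recovery from one, can therefore be credited to BBL or hide a BBL effect.

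The size is not calculable from the documents. The illustration rests on assumed numbers exposed, shifts, correlation and 20 swabbed patients. On those inputs, one or two exposed patients hardly move a mean-diversity test, and larger numbers matter more if their shifts run the same way.

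Only the microbiome portion is affected. No effect on safety, symptom scores or the clinical dry-eye measures has been shown. The change is worth making because it is cheap and because undated exposure may be lost for good.

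**What to change.** 1. **Data collection.** At screening and at each existing visit, record any systemic, eye, lid or facial antibiotic use: drug, route, start date and stop date. Cover the period from one month before the baseline swab to the follow-up swab.
2. **SAP.** Pre-specify that the before/after microbiome analyses (diversity, PERMANOVA, ZINB and random forest) are repeated without swab pairs from patients who used such an antibiotic in the month before either swab. Keep pairs where an antibiotic was continued unchanged throughout. Report both sets of results. The one-month window is borrowed from the plan's doxycycline criterion as an analysis convention, not as a claim about recovery time.
3. **Eligibility.** Leave to the sponsor and investigator whether Protocol 3.4 should be widened.

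The cost is one extra question per visit, a short addition to the SAP, and a few swab pairs dropped from the repeat analysis, which will be somewhat less precise. Enrolment is unaffected.
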